7.2 Secondary endpoints

7.2.1 Confirmatory secondary endpoints

The binary confirmatory secondary outcomes include:

- **Remission**, defined as a CDRS-R total score < 28 at any time up until 36 weeks
- **Response**, defined as a 30% drop in CDRS-R total score at any time up until **12 weeks**
- **Intervention dropout**, defined as initiation of non-randomized antidepressant use while on trial for participants not on a non-randomized antidepressant at baseline or an increase in antidepressant dose while on trial for participants on a non-randomized antidepressant at baseline

Unadjusted proportions per treatment arm will be presented with 95% confidence intervals. To adjust for baseline antidepressant use, omega-3 index, and CDRS score, as well as the minimization factors age, gender, and hsCRP, these binary outcomes will each be assessed using log-binomial models with treatment arm as the effect of interest. Each model will be interpreted in terms of the adjusted risk ratio (RR) comparing the outcome probability in the omega-3 group to that in the placebo group ($RR_{\text{omega-3/placebo}}$). The null hypothesis that the risk ratio is equal to 1 (no difference in risk across treatment groups) will be rejected if the 95% confidence interval for the risk ratio does not include 1. If the 95% confidence interval for the risk ratio is above 1, omega-3 treatment will be considered superior.

These models will include data from all randomized participants and analyze the participant data according to the treatment arms participants were randomized to (as-randomized). Data after intervention dropout will be considered missing. Multiple imputation under MAR will be used to impute longitudinal CDRS-R scores for study and intervention dropouts before the binary outcomes are determined. MI will be performed separately within each treatment arm (White et al 2011) using imputation models containing the minimization factors, baseline antidepressant use and omega-3 index.

As for the primary outcome, a delta-based sensitivity analysis approach will be used to address MNAR. For analysis of intervention dropout, imputation is only needed for participants with study dropout before intervention dropout and no sensitivity analysis is planned.

The continuous confirmatory secondary outcomes include:

- self-reported **quality of life** measured by the KIDscreen-CAT-27 overall score at 36 weeks
- **Depression severity** measured by DIKJ at 36 weeks

These continuous outcomes will each be assessed using ANCOVA linear regression models with the 36-week measurement as the outcome, treatment arm as the effect of interest, and the baseline measurement, antidepressant use, omega-3 index, CDRS-R score, and the minimization factors age, gender, and hsCRP as covariates.

The treatment coefficient denotes the mean difference in outcome score across the treatment groups. The null hypothesis that the mean scores are equal across treatment groups will be rejected

if the 95% confidence interval for the treatment group coefficient does not include 0. If the 95% confidence interval for the treatment group coefficient is above 0 for KIDscreen-CAT-27 (below 0 for DIKJ), omega-3 treatment will be considered superior with respect to its effect on quality of life (depressive symptoms).

These models will include data from all randomized participants and analyze the participant data according to the treatment arms participants were randomized to (as-randomized). Data after intervention dropout will be considered missing. Multiple imputation under MAR will be used to impute scores at 36 weeks for study and intervention dropouts. MI will be performed separately within each treatment arm (White et al 2011) using imputation models containing the minimization factors, baseline antidepressant use, omega-3 index, and baseline score. As for the primary outcome, a delta-based sensitivity analysis approach will be used to address MNAR.

Sub-domains will be described with tables or figures.

The final confirmatory secondary outcome is:

- the time on trial before initiation of new or increased antidepressant use (intervention dropout).

A Kaplan Meier approach will be used to estimate unadjusted median time to this event overall and per treatment arm. A log rank test will be used to compare time to intervention dropout across treatment arms.

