5.2 Secondary Outcomes

WH 2a – We hypothesize that more pMDD patients in the placebo group will be put on antidepressant medication compared to the Omega-3 fatty acids group.

WH 2b – We hypothesize that the Omega-3 fatty acids group will achieve a higher level of functioning (a higher CGAS score) and a better quality of life (overall and within the five dimensions as assessed with KIDscreen-CAT -27) compared to the placebo group.

WH 2c – We hypothesize that the Omega-3 fatty acids group will spend fewer days in hospital and will have a lower outpatient service use (measured with the attrition check list) compared to the placebo group also resulting in a reduction in overall costs (calculated via TARMED points).

WH 2d – We hypothesize that the overall retention rate will be higher in the Omega-3 fatty acids group compared to the placebo group (or, in other words the placebo group will have more and earlier drop outs due to lack of efficacy). This hypothesis will be tested by two means: 1.) in the ITT sample independent if they received an antidepressant in the due course of the trial, as well as 2.) in a modified ITT sample, where those subjects that are put on an antidepressant will be considered as drop-outs from the day they received the first dose of an antidepressant.

WH 3a – Based on the recent meta-analysis [62] showing increased inflammatory mediators in adult MDD, we assume that at least 50% of participants will have a baseline increase of inflammatory mediators (in particular hsCRP, IL-1, IL-6) and a decrease of anti-inflammatory markers (IL-10). Based on a recent Omega-3 fatty acids treatment study in adult MDD [63], we hypothesize that Omega-3 fatty acid response will be predicted by the ratio between pro- and anti-inflammatory markers.

WH 3b – Based on the meta-analysis by Lin et al [54] as well as the study of Potalla et al [61] in pMDD, we hypothesize that about 80% of participants with pMDD will have a reduction in red blood cell Omega-3 fatty acids content, in particular EPA and DHA (used to calculate the Omega-3 index® [207, 208]). We hypothesize that those with an omega-3 index® <4 at baseline will benefit more from Omega-3 fatty acids treatment, whereas those with an omega-3 index >5 (approx. 20%) will not show a marked benefit from Omega-3 fatty acids treatment. We further hypothesize that a high n-6/n-3 Omega ratio at baseline will be associated with a better response to Omega-3 fatty acids.

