Omega-3 Fatty Acids as First-Line Treatment in Pediatric Depression

Statistical Analysis Plan for [name], [name]

[name] ([contact])

[name]

Version 1.0 of May 23, 2022

List of abbreviations

AD	antidepressant
AE	adverse event
CDRS-R	Children's Depression Rating Scale - Revised
DIKJ	Children's Depression Inventory (Depressionsinventar für Kinder und Jugendliche)
EPA	eicosapentaenoic acid
KIDscreen-CAT-27	quality of life questionnaire
pMDD	pediatric major depressive disorder
SIQ-Jr	Suicide Ideation Questionnaire-Junior
SUSAR	Suspected Unexpected Serious Adverse Reaction

Introduction

1 Type of trial

This is a 36-week multi-center 1:1 randomized, double-blind, placebo-controlled, two-armed, parallel group study investigating the superiority of EPA-rich Omega-3 to placebo in the treatment of children and adolescents with pediatric major depressive disorder. The randomization included a minimization algorithm based on the following factors: site, age (8-12 vs. 13-18), gender (male vs. female), and hsCRP (<1 mg/l; 1-3 mg/l; >3mg/l). For sites offering both in- and out-patient care, in-/out-patient type was used as an additional minimization factor. The trial aimed to recruit children/teenagers between 8 and 18 years old with a primary diagnosis of major depressive disorder (DSM-IV, K-SADS-PL) and at least moderate depressive symptoms (CDRS-R ≥ 40).

In order to include a representative sample of moderately and severely ill children with major depressive disorders, the use of clinically required SSRIs is permitted. The anticipated proportion of patients receiving additional antidepressants at some point during follow-up is estimated to be around 30%. The use of additional antidepressants is expected to influence primary outcome measurements and be influenced by treatment group, with greater antidepressant use hypothesized in the control arm. Antidepressant use may therefore bias the estimation of the omega-3 treatment effect.

2 Scope of the statistical analysis plan

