5.2 Secondary endpoints

5.2.1 Confirmatory secondary endpoints

- Remission (CDRS-R total score less than or equal to 28) at any point during the 36 weeks of trial observation
- Response (30% reduction in CDRS-R total score) at any point within 12 weeks from baseline
- Participants newly initiating antidepressant medication (or newly increasing dose if on antidepressant at baseline) at any point during the 36 weeks of trial observation
- Number of days on trial before new antidepressant initiation (or new antidepressant dose increase if on antidepressant at baseline)
- KIDscreen-CAT-27 overall quality of life score at 36 weeks
- DIKJ depression score at 36 weeks

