6.2 Difference in Proportion of Responders

A two-proportion z-test would require 97 participants per treatment arm to have 80% power to detect a difference in response of 20% (with 60% response in the treatment group and 40% response in the control group) at the 0.05 two-sided significance level. Accounting for a 10% loss to follow-up results in a total sample size of 216 participants.

7 Statistical analyses

Analysis sets The following analysis sets are defined in accordance with the ICH-E9 guidelines:

- The full analysis set (FAS) includes all randomized subjects. The FAS will be used for 'as randomized' evaluation. Only in exceptional cases may subjects be excluded from the FAS. In such cases the reason for exclusion will be justified and documented.
- The safety analysis set includes all randomized subjects receiving at least one dose of randomized treatment. The safety analysis set will be used for 'as treated' evaluation.

Baseline comparability of randomized groups Baseline descriptive variables of participants (including antidepressant use) will be summarized overall and by treatment arm using suitable measures of central tendencies and variability for continuous data (means or medians, SD or IQR) and frequencies and proportions for categorical data. No hypotheses are tested.

The number of participants lost to follow-up, initiating antidepressants, and adhering to the protocol will each be tabulated by treatment arm and visit. Baseline characteristics will also be summarized across the groups of participants completing the trial, lost to follow-up, and initiating antidepressant use.

General statistical considerations Statistical analysis results will generally be presented as point estimates with two-sided 95% confidence intervals. A limited number of analysis results will additionally be reported with p -values, which will be interpreted as indicative of superiority when the value is less than 5% and the estimated treatment contrast favors the omega-3 treatment arm.

Descriptive statistics for all efficacy and safety endpoints will be presented according to treatment arm.

The baseline values are collected at visit 1 (0 weeks), which is the first week after the lead-in phase. Further measurements are taken at visits 2 through 5 at 6, 12, 24, and 36 weeks.

The clinical trials registry number (03167307) will be used as a seed number, if needed.

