7.1.2 Sensitivity analyses for the primary endpoint

1. **Typical ITT analysis:** In order to compare results with other trials, the linear mixed model part of the analysis model above will be applied to the full analysis set, with all participants analyzed as randomized. The data from intervention dropout participants will be used as observed, i.e, the outcomes observed while on non-randomized antidepressants will be used. The mixed model assumes that missing data is missing at random. This analysis is expected to be biased toward the placebo arm, as the number of participants requiring antidepressants is expected to be higher in the placebo arm and the additional antidepressant will improve outcomes.
2. **Modified ITT analysis:** The first sensitivity analysis will be repeated, but the data from intervention dropout participants will be considered missing in the mixed model upon non-randomized antidepressant initiation/dose increase. The responses of participants with missing data will be assumed similar to those with complete data and similar covariate characteristics. The bias resulting from imbalance in the use of non-randomized antidepressants across treatment groups is curtailed, but the amount of data available for analysis, and therefore power, is diminished.
3. **Typical PP analysis:** In order to address the efficacy estimand, the sensitivity analysis model above will be applied to all full analysis set data during which participants were 'on protocol'. This means the participants are adhering to the treatment they were randomized to and are not using additional antidepressants. Non-compliers and those taking non-randomized antidepressants are excluded completely (i.e., complete case analysis). This yields an estimate of efficacy that is unbiased under the MAR assumption. It assumes that participants with missing data (those with additional antidepressants and those not adhering to randomized treatment) would have had similar outcomes to participants completing the study in the same treatment arm and with similar baseline characteristics and score trajectories. However, the use of additional anti-depressants is not considered to be random across participants, but rather related to intermediate outcomes and possibly treatment assignment. Selection bias is then expected to affect this estimate. Additionally, the reduction in participants decreases the power to detect a treatment effect.

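### The superiority rule for the binary confirmatory endpoints points the wrong way for antidepressant initiation, and the SAP gives two remission cut-offs

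*SAP*

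**What the plan says.** SAP 7.2.1 names three binary confirmatory outcomes: remission, response and intervention dropout. The third is "defined as initiation of non-randomized antidepressant use while on trial", or a dose increase for participants already on an antidepressant at baseline. Each outcome gets its own log-binomial model, and each model is read through the adjusted risk ratio with omega-3 in the numerator and placebo in the denominator. The null is rejected when the 95% interval excludes 1. The verdict rule follows, with no outcome excepted: "If the 95% confidence interval for the risk ratio is above 1, omega-3 treatment will be considered superior".

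The expected direction for antidepressant use is stated three times. Protocol 5.2 (WH 2a) hypothesises that "more pMDD patients in the placebo group will be put on antidepressant medication". SAP section 1 permits antidepressants "with greater antidepressant use hypothesized in the control arm". SAP 7.1.2 says that "the number of participants requiring antidepressants is expected to be higher in the placebo arm".

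Two other SAP statements bear on direction. The general considerations in section 7 say that p-values will be "interpreted as indicative of superiority when the value is less than 5% and the estimated treatment contrast favors the omega-3 treatment arm". For the continuous confirmatory endpoints, 7.2.1 sets the direction outcome by outcome: above 0 for quality of life, but "below 0 for DIKJ), omega-3 treatment will be considered superior".

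On remission, the SAP 5.2.1 endpoint list has "Remission (CDRS-R total score less than or equal to 28) at any point", while SAP 7.2.1 uses a score strictly below 28.

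**The concern.** A risk ratio above 1 means that the event is more frequent on omega-3. That is good for remission and response and bad for starting or increasing an antidepressant. One rule cannot serve both kinds of event. For intervention dropout the written rule is reversed: it gives no credit to the result the trial hopes for and labels the opposite result as superiority.

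The stake is the stated verdict on an endpoint that the SAP calls confirmatory and that tests WH 2a. A pre-specified decision rule should not have to be reinterpreted once the direction of the data is known.

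The split cut-off is a lesser matter of the same kind: the reported remission rate depends on which SAP section is programmed.

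**Working it through.** **The plan's own figure.** The only sample size stated for a binary confirmatory endpoint is the responder calculation in SAP 6.2 (60% v 40%, two-sided 5%, 80% power):

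n = [1.96·√(2·0.5·0.5) + 0.842·√(0.6·0.4 + 0.4·0.6)]² / 0.20² = (1.386 + 0.583)² / 0.04 ≈ 97 per arm.

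With 10% loss, 97/0.9 = 107.8, so 108 per arm and 216 in total. This agrees with the SAP and is not in dispute.

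**Direction of each binary outcome against the rule.**

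| Outcome (SAP 7.2.1) | Direction that favours omega-3 | Written rule | Agrees? |
|---|---|---|---|
| Remission | RR > 1 | CI above 1 | yes |
| Response | RR > 1 | CI above 1 | yes |
| Intervention dropout | RR < 1 (Protocol WH 2a; SAP 1; SAP 7.1.2) | CI above 1 | no |

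**One data set through the rule.** Take 110 per arm (Protocol synopsis), with 41 events on omega-3 and 25 on placebo. The total is 66/220 = 30%, the overall rate in SAP section 1.

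- ln RR = ln(41/25) = 0.4947
- SE = √(1/41 − 1/110 + 1/25 − 1/110) = √0.0462 = 0.2150
- 95% CI = exp(0.4947 ± 1.96 × 0.2150) = 1.08 to 2.50, around RR 1.64

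The rule says omega-3 is superior, with 16 more participants on omega-3 starting or increasing antidepressants. Swap the arms and RR is 0.61 (0.40 to 0.93). The null is rejected, but the rule gives no superiority verdict.

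**How often this could matter.** The documents give about 30% antidepressant use overall and no rates by arm, so the splits below are assumptions centred on 30%. For each split, the binomial probabilities of all event-count pairs whose Wald interval on the log risk ratio lies wholly below 1 were added up (exact enumeration, unadjusted, complete data). The 120 per arm column allows for the up to 20 additional participants in Protocol 6.2.

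| True rate, omega-3 v placebo | P(CI below 1), 110 per arm | 120 per arm |
|---|---|---|
| 28% v 32% | 9% | 9% |
| 25% v 35% | 36% | 38% |
| 24% v 36% | 49% | 52% |
| 22% v 38% | 73% | 77% |
| 20% v 40% | 90% | 92% |

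The written rule calls none of these results superior. By symmetry, with the rates reversed, the same percentages are the chance of a false superiority verdict. With no difference (30% v 30%) that chance is about 2.4% at 110 per arm.

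**Remission cut-off.**

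| Place | Cut-off |
|---|---|
| SAP 5.2.1 | ≤28 |
| SAP 7.2.1 | <28 |
| Protocol 5.1 | ≤28, together with the K-SADS interview |
| Protocol 9.2.1 | ≤28 for remission; <28 for recovery |
| Protocol 11.4.3 | <28 |

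CDRS-R totals are whole numbers, so only a participant whose lowest post-baseline score is exactly 28 changes class. The documents give no score distribution. Simulating four post-baseline visits with rounded normal scores (400,000 participants per setting, between-visit correlation 0.3 to 0.7) gives:

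- assumed mean/SD of 32/12, 35/13 or 38/14: 3.1% to 3.6% of participants;
- assumed mean 45 or 50, SD 14: 1.7% to 3.2%.

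That is roughly 4 to 8 of 220. At 35/13 and correlation 0.5, remission is 60.1% with ≤28 and 56.6% with <28.

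**The case against.** The best reply is that this is a drafting slip whose intent nobody would mistake. The documents state the expected direction three times, the SAP's general wording asks for a contrast that favours omega-3, the null is tested two-sided, and a log-rank test covers the same event. A risk ratio of 0.61 with its interval would still be reported and understood.

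Much of that stands. Estimates, intervals and tests are unaffected, and the practical risk is modest. But the general wording concerns the limited set of results reported with p-values, whereas 7.2.1 gives a specific interval rule for these endpoints; the two conflict, and the SAP does not say which governs. Nor does the SAP leave direction to common sense elsewhere: it reverses the sign explicitly for DIKJ in the same section.

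It is also fair to say that the percentages above are the power of the correctly directed test under assumed splits. They are not the chance that someone would publish the wrong verdict. Small splits give small figures, the false-verdict range needs omega-3 to increase antidepressant use, and the planned analysis is covariate-adjusted with multiple imputation. The logical point does not depend on any of these numbers.

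On remission, two of the protocol places are not clean contradictions. The <28 in Protocol 9.2.1 belongs to recovery, which the SAP has dropped, and Protocol 5.1 adds a diagnostic interview. The conflict between SAP 5.2.1 and SAP 7.2.1 remains, with Protocol 11.4.3 on the side of 7.2.1.

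**Conclusion.** The point holds. As written, SAP 7.2.1 reverses the superiority verdict for intervention dropout, a confirmatory endpoint. This follows from the text alone and needs no assumption.

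Its size depends on unknown rates by arm. At 110 per arm, a real benefit would produce an interval wholly below 1 in 9% of trials for a 4-point difference and in 36% to 90% for differences of 10 to 20 points, and the rule would credit none of them. The rule is right for remission and response, and the primary analysis is untouched.

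The remission cut-off is inconsistent within the SAP. It is a minor matter: about 2% to 4% of participants under assumed score distributions, with the same definition applied to both arms. It should be fixed, but it does not add to the seriousness of the first point.

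**What to change.** In SAP 7.2.1, state the direction for each outcome. For remission and response, omega-3 is superior if the whole 95% interval for the omega-3/placebo risk ratio is above 1. For intervention dropout, it is superior only if the whole interval is below 1.

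State one remission cut-off in SAP 5.2.1 and 7.2.1, for example the ≤28 of the endpoint list, and note that it replaces the <28 in Protocol 11.4.3.

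Make both changes before the analysts receive the randomisation code. The SAP is dated 23 May 2022, the planned database closure was April 2022, and the documents do not give the actual unblinding date. If the code has already been released, record the changes as a dated correction to the SAP and say so in the report.

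The cost is two SAP sentences. No data, participants or analyses are added, and no sample size changes.

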where time t is considered a factor (while also investigating possibility of linearizing time effect) and randomized treatment group (intervention) and the interaction between randomized treatment group and time are included as fixed effects. The baseline values of the minimization factors age, gender, and hsCRP, as well as baseline antidepressant use and omega-3 index are included as covariates. The baseline outcome measure is modeled in the response, not as a covariate. The terms b_{i0} , b_{i1} , and b_{s0} represent participant-specific random intercepts and slopes and site-specific random intercepts. The random effects are assumed to be normally distributed and an unstructured covariance matrix will be assumed. The error term $\varepsilon_i(t)$ is assumed to be normally distributed with mean zero and variance σ^2 , independent of the random effects and is independent over time. An overall treatment effect for CDRS-R score at 36 weeks ($\beta_1 + \beta_{11}$) will be reported with a 95% confidence interval and corresponding p -value.

The competing survival models for time to event r (intervention dropout or study dropout) take the form:

$$\lambda_{ir}(t) = \lambda_{0r} \exp\{\gamma_1 \text{intervention} + \alpha_r m_i(t)\}$$

where the cause-specific Cox models include intervention as a time-independent effect and the estimated true trajectory of CDRS-R as a time-varying effect. The parameters α_r measure the strength of association between the longitudinal outcome and risk of the corresponding dropout event.

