4. **Delta-based multiple imputation for MNAR analysis:** The data after intervention dropout or study dropout is considered to be missing. Multiple imputation under MAR will be performed separately within each treatment arm (White et al 2011) using imputation models containing the minimization factors, baseline antidepressant use and omega-3 index. It will be assumed that participants initiating/increasing non-randomized antidepressant use would have had worse outcomes than observed had they not used the non-randomized antidepressant. A range of mean differences δ from a 25% increase in CDRS-R score (25% worse outcome) to a 100% increase (by 25% increments) in the CDRS-R score in the intervention dropouts as compared to the observed cases will be considered. Delta will then be added to the imputed

CDRS-R scores for the participants with intervention dropout. Results will be combined using Rubin's rule. This is repeated for each delta.

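### The imputation model listed for longitudinal CDRS-R contains no CDRS-R score and no patient term; followed as listed, it overstates any-visit remission and, to a lesser degree, response

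*SAP*

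**What the plan says.** SAP 5.2.1 defines two confirmatory secondary endpoints as events at any visit: "Remission (CDRS-R total score less than or equal to 28) at any point during the 36 weeks of trial observation" and "Response (30% reduction in CDRS-R total score) at any point within 12 weeks from baseline". (SAP 7.2.1 writes the remission cut-off as strictly below 28; the two should be reconciled. I use the 5.2.1 form.) The visit schedule is in SAP 7, general statistical considerations: "Further measurements are taken at visits 2 through 5 at 6, 12, 24, and 36 weeks". Remission therefore has four chances to occur and response two.

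SAP 7.2.1 treats data after an antidepressant start or dose increase as missing and continues: "Multiple imputation under MAR will be used to impute longitudinal CDRS-R scores for study and intervention dropouts before the binary outcomes are determined". The imputation is done "separately within each treatment arm (White et al 2011) using imputation models containing the minimization factors, baseline antidepressant use and omega-3 index". SAP 7.1.2 item 4, the delta-based sensitivity analysis of the primary endpoint, repeats the list: "using imputation models containing the minimization factors, baseline antidepressant use and omega-3 index".

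Three other places in the SAP bear on this:

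- For KIDscreen and DIKJ at week 36, 7.2.1 imputes "using imputation models containing the minimization factors, baseline antidepressant use, omega-3 index, and baseline score". The CDRS-R list lacks that last item.
- The log-binomial model for remission and response adjusts for baseline CDRS-R, so the imputation list omits a covariate of its own analysis model.
- The primary model in 7.1 has terms that "represent participant-specific random intercepts and slopes and site-specific random intercepts". The imputation text has no counterpart.

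SAP 7 gives 50 imputations and Rubin's rule but no algorithm. The 2011 source cited for imputing within arm is not in the SAP's reference list.

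**The concern.** Two separate things go wrong if the list is used as it stands.

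First, within-patient correlation is lost. Given a few baseline variables, each missing visit is drawn afresh. An any-visit event built from unrelated draws is too frequent even when every single visit has the right mean and variance, because a patient who stays unwell gets several unconnected chances to cross the cut-off.

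Second, the predictors of missingness are left out. SAP 7.1.2 item 3 says that antidepressant use is related to intermediate outcomes. Patients who start are then those with poor earlier scores, but the listed model imputes them like an average patient of their arm. MAR needs those scores in the model.

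Response has a further problem. Its threshold is 70% of the patient's own baseline, and baseline is not in the list either.

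At stake are the remission and response rates in both arms and their risk ratios. SAP 1 expects more antidepressant starts in the control arm, so the error need not cancel.

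**Working it through.** **1. The plan's own figure.** SAP 6.2 sizes response at 60% v 40%, 80% power, two-sided 0.05:

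n = [1.960·√(2·0.5·0.5) + 0.842·√(0.6·0.4 + 0.4·0.6)]² / 0.20² = (1.386 + 0.583)² / 0.04 = 96.9, so 97 per arm. Then 97/0.9 = 107.8, so 108 per arm and 216 in total.

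This agrees with the SAP. The SAP gives no figure for the imputation.

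**2. How many patients are exposed.** SAP 1 expects about 30% to start an antidepressant. Protocol 6.2 reports 21 of 225 randomised patients lost before the first follow-up, and Protocol 6.3.2 about 20 antidepressant starts before week 6. If the groups do not overlap, 41/225 = 18% have no usable post-baseline CDRS-R, and all their visits are imputed.

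**3. Lost correlation alone.** Assume remission at single visits of 5, 10, 20 and 30%. If visits are independent, the any-visit rate is 1 − 0.95·0.90·0.80·0.70 = 52%. With equal correlation 0.3, 0.5 or 0.7 between visits (multivariate normal) it is 46, 41 or 37%. For response with assumed 30 and 40% at two visits, independence gives 1 − 0.70·0.60 = 58%, against 54, 51 or 47%. These gaps apply only to patients with every visit imputed.

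**4. Whole-arm effect by simulation** (400,000 patients drawn per arm). None of the following is in the documents: baseline mean 55, SD 9, kept if at least 40; visit SD 11; visit means 45, 42.5, 40, 38 (placebo) and 41.5, 38.5, 36.5, 35 (omega-3); listed covariates explaining 5% of variance; the split of starts by arm. Starts were either random or driven by the previous score. Missing visits were imputed within arm from the listed covariates only. All results are placebo / omega-3.

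| Correlation, starts | Split | True remission | As listed | Risk ratio |
|---|---|---|---|---|
| 0.5, random | 35/25 | 27.6 / 40.9% | 30.3 / 44.1% | 1.48 → 1.45 |
| 0.5, score-driven | 35/25 | 27.6 / 40.7% | 34.7 / 47.7% | 1.47 → 1.37 |
| 0.7, random | 30/30 | 22.7 / 34.6% | 25.9 / 39.6% | 1.52 → 1.53 |
| 0.7, random | 35/25 | 22.7 / 34.7% | 26.3 / 39.2% | 1.53 → 1.49 |
| 0.7, score-driven | 30/30 | 22.7 / 34.6% | 30.0 / 45.2% | 1.52 → 1.51 |
| 0.7, score-driven | 35/25 | 22.8 / 34.7% | 31.4 / 43.5% | 1.52 → 1.38 |

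The overstatement is mostly 3 to 4 points with random starts (largest 39.6 − 34.6 = 5.0) and 7 to 9 with score-driven starts (largest 45.2 − 34.6 = 10.6).

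The random rows isolate the lost correlation. At correlation 0.7 and 35/25 it accounts for 3.6 of the 8.6 placebo points; the other 5.0 come from omitting the scores that drive starts. In that scenario true remission among placebo starters is 9.3%, and the list gives 32.2%.

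**5. Response, correlation 0.7.**

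| Starts | Split | True response | As listed | Risk ratio |
|---|---|---|---|---|
| random | 30/30 | 39.0 / 59.8% | 41.6 / 61.3% | 1.53 → 1.47 |
| random | 35/25 | 38.9 / 60.2% | 41.8 / 61.5% | 1.55 → 1.47 |
| score-driven | 30/30 | 38.9 / 60.1% | 45.3 / 65.2% | 1.54 → 1.44 |
| score-driven | 35/25 | 38.9 / 60.0% | 46.2 / 64.3% | 1.54 → 1.39 |

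The last row is close to the planning rates. Crude two-proportion power at 108 per arm falls from 88% to 77%; this ignores imputation variance and covariate adjustment. At a true response of about 86% with random starts there is no bias.

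**6. With CDRS-R in the model.** Adding baseline and all earlier CDRS-R scores brings the overall rates back to within about 0.3 points of truth in every scenario. For correlation 0.5, score-driven, 35/25, remission becomes 27.7 / 40.8% (ratio 1.47). Adding baseline alone gives 30.5 / 43.7% (ratio 1.43), a partial repair.

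**The case against.** The strongest reply is that the SAP does not say the list is complete. It speaks of imputing longitudinal scores with models that contain certain variables. Standard chained equations on one row per patient, or a multivariate normal model, would let the visits predict each other, with the listed items as added covariates. The primary model in 7.1 also treats baseline as part of the response, so the CDRS-R series may be taken as understood. The KIDscreen and DIKJ text imputes a single week-36 score, so baseline has to be named there. This stands in part. A reader might infer that the SAP deliberately draws visits independently; the text does not support that. What it supports is that the model is not specified and that the list, if followed, has this effect.

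A reader might also infer that the overstatement is always largest in the arm with more starts. In percentage points it is not: with random starts at 35/25 and correlation 0.5 it is 2.7 points in placebo and 3.2 in omega-3. The statement holds for the ratio, or when the true rates are equal.

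The delta analysis that 7.2.1 plans for these endpoints is a partial safeguard. If the increments are read as percentages of the imputed score, at 75% a score would have to be 28/1.75 = 16 or less to count as remission, below the scale minimum of 17 (Protocol 9.2.1). That tests over-imputed remission among antidepressant starters. It does not restore the within-patient correlation, and it leaves the imputed scores of study dropouts as they are.

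**Conclusion.** The point holds as a gap in specification with a material consequence if the list is followed. Under the assumptions above, remission is overstated in both arms, by about 2 to 4 points with random starts and about 6 to 10 with score-driven starts, with single values slightly beyond. Response is overstated less: by 1.3 to 2.9 points with random starts at correlation 0.7, and not at all at a high response rate. If placebo has more starts, the remission ratio is pulled toward 1; with equal starts it changes little. The response ratio at correlation 0.7 falls somewhat even with equal starts.

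Two stronger conclusions are not supported. A reader might infer a fixed and large loss of power, but the documents give no split of starts by arm, and a large loss needs a marked imbalance or strongly score-driven starts. A reader might also infer a raised risk of a false claim for omega-3. If there is no true effect and placebo has more starts, the remission ratio falls below 1 (0.93 at correlation 0.7, score-driven, 35/25), whereas 7.2.1 requires an interval above 1 for superiority.

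The primary joint model does not use this imputation and is unaffected. Two confirmatory secondary endpoints and one sensitivity analysis of the primary endpoint are affected; the effect on that sensitivity analysis was not quantified.

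**What to change.** In SAP 7.2.1 and in 7.1.2 item 4, replace the list with a statement along these lines: CDRS-R at baseline and weeks 6, 12, 24 and 36 will be imputed jointly within each arm, by chained equations or a multivariate normal model in which all visits predict each other, or by a multilevel model with patient random intercept and slope; the minimization factors, baseline antidepressant use and omega-3 index enter as further covariates; remission and response are derived from each imputed trajectory. Name the algorithm and correct the 2011 citation or add it to the reference list.

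Baseline CDRS-R alone is not enough, as step 6 of the working shows. The cost is SAP wording and a few lines of code, with no new data. The only downside is a slightly larger imputation model, five correlated scores per arm, which about 110 patients per arm can support.
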